- Any clinically relevant, abnormal laboratory test results (hematology, clinical chemistry, or urinalysis), or other safety assessments (e.g., ECG, radiological scans, vital sign measurements), including those that worsen from baseline. Refer to Section 8.2.4 for reporting requirements of abnormal laboratory results as adverse events.
- Exacerbation of a chronic or intermittent preexisting condition, including either an increase in frequency and/or intensity of the condition
- New condition detected or diagnosed after study treatment administration, even though it may have been present before the start of the study
- Signs, symptoms, or clinical sequelae of a suspected drug–drug interaction
- Signs, symptoms, or clinical sequelae of a suspected overdose of either study treatment or a concomitant medication
 - Overdose per se will not be reported as an adverse event or serious adverse event unless it is an intentional overdose taken with possible suicidal or self-harming intent. Such overdoses should be reported regardless of sequelae.
- "Lack of efficacy" or "failure of expected pharmacological action" per se will not be reported as an adverse event or serious adverse event. Such instances will be captured in the efficacy assessments. However, the signs, symptoms, and/or clinical sequelae resulting from lack of efficacy will be reported as an adverse event or serious adverse event if they fulfill the definition of an adverse event or serious adverse event.

Appendix 3: Adverse Events: Definitions and Procedures for Recording, Evaluating, Follow-Up, and Reporting

Events NOT Meeting the Definition of Adverse Event

The following events do not meet the definition of adverse event:

- Any clinically significant abnormal laboratory findings or other abnormal safety assessments that are associated with the underlying disease, unless judged by the investigator to be more severe than expected for the patient's condition
- The disease or disorder being studied or expected progression, including MS relapses, signs, or symptoms of the disease or disorder being studied, unless more severe than expected for the patient's condition
- Medical or surgical procedure (e.g., endoscopy, appendectomy)
The condition that leads to the procedure is the adverse event.
- Situations in which an untoward medical occurrence did not occur (social and/or convenience admission to a hospital)

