- Anticipated day-to-day fluctuations of a preexisting disease or condition present or detected at the start of the study that do not worsen

A3–2. DEFINITION OF SERIOUS ADVERSE EVENT

If an event is not an adverse event per the definition in Section [A3–1](#), it cannot be a serious adverse event even if serious conditions are met (e.g., hospitalization for signs or symptoms of the disease under study, death due to progression of disease).

A serious adverse event is defined as any untoward medical occurrence that, at any dose:

- Results in death
- Is life threatening

The term "life-threatening" in the definition of "serious" refers to an event in which the patient was at risk of death at the time of the event. It does not refer to an event that hypothetically might have caused death if it were more severe.

- Requires inpatient hospitalization or prolongation of existing hospitalization

In general, hospitalization signifies that the patient has been detained (usually involving at least an overnight stay) at the hospital or emergency ward for observation and/or treatment that would not have been appropriate in the physician's office or outpatient setting. Complications that occur during hospitalization are adverse events. If a complication prolongs hospitalization or fulfills any other seriousness criteria, the event is serious. When in doubt as to whether "hospitalization" occurred or was necessary, the adverse event should be considered serious.

Hospitalization for elective treatment of a preexisting condition that did not worsen from baseline is not considered an adverse event.

Appendix 3: Adverse Events: Definitions and Procedures for Recording, Evaluating, Follow-Up, and Reporting

- Results in persistent disability or incapacity

The term "disability" means a substantial disruption of a person's ability to conduct normal life functions.

This definition is not intended to include experiences of relatively minor medical significance such as uncomplicated headache, nausea, vomiting, diarrhea, influenza, and accidental trauma (e.g., sprained ankle) that may interfere with or prevent everyday life functions but do not constitute a substantial disruption.

- Is a congenital anomaly or birth defect
- Other situations:

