Observations of the same clinically significant vital sign abnormality from visit to visit should only be recorded once on the Adverse Event eCRF (see Section A3-7.4 for details on recording persistent adverse events).

A3-7.6 ABNORMAL LIVER ENZYMES AND FUNCTION TESTS

An elevated ALT and/or AST ($>3 \times \text{ULN}$) must be reported as an adverse event in this protocol (refer to table A6-1).

- *Cases of potential drug-induced liver injury that include an elevated ALT or AST ($>3 \times \text{ULN}$) in combination with either an elevated total bilirubin ($>2 \times \text{ULN}$) or clinical jaundice, as defined by Hy's Law (refer to Table A6-1).*
- *Cases of elevated ALT and/or AST $3-5 \times \text{ULN}$, $\text{INR} > 1.5$, total bilirubin $\leq 2 \times \text{ULN}$, and absence of clinical jaundice*
- *Cases of elevated ALT and/or AST $5-8 \times \text{ULN}$, total bilirubin $\leq 2 \times \text{ULN}$ and absence of clinical jaundice*
- *Cases of ALT or AST $> 8 \times \text{ULN}$, total bilirubin $\leq 2 \times \text{ULN}$ and absence of clinical jaundice*

The most appropriate diagnosis or (if a diagnosis cannot be established) the abnormal laboratory values should be recorded on the Adverse Event eCRF (see Section A3-7.2) and reported to the Sponsor immediately (i.e., no more than 24 hours after the investigator becomes aware of the event), either as a serious adverse event or an adverse event of special interest (see Section A3-5).

Appendix 3: Adverse Events: Definitions and Procedures for Recording, Evaluating, Follow-Up, and Reporting

Abnormal liver enzymes will warrant close observation and ruling out of alternative causes (refer to [Table A6-1](#) and [Appendix 7](#)).

A3-7.7 DEATHS

All deaths that occur during the protocol-specified adverse event reporting period (see Section [8.3.1](#)), regardless of relationship to study treatment, must be recorded on the Adverse Event eCRF and immediately reported to the Sponsor (see Section [A3-5](#)). This includes death attributed to an MS relapse.

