Death should be considered an outcome and not a distinct event. The event or condition that caused or contributed to the fatal outcome should be recorded as the single medical concept on the Adverse Event eCRF. Generally, only one such event should be reported. If the cause of death is unknown and cannot be ascertained at the time of reporting, "**unexplained death**" should be recorded on the Adverse Event eCRF. If the cause of death later becomes available (e.g., after autopsy), "unexplained death" should be replaced by the established cause of death. The term "**sudden death**" should not be used unless combined with the presumed cause of death (e.g., "sudden cardiac death").

If the death is attributed solely to progression of multiple sclerosis, "multiple sclerosis progression" should be recorded on the Adverse Event eCRF. Deaths that occur after the adverse event reporting period should be reported as described in Section [A3-6](#).

A3-7.8 PREEXISTING MEDICAL CONDITIONS

A preexisting medical condition is one that is present at the screening visit for this study. Such conditions should be recorded on the General Medical History and Baseline Conditions eCRF.

A preexisting medical condition should be recorded as an adverse event only if the frequency, severity, or character of the condition worsens during the study. When recording such events on the Adverse Event eCRF, it is important to convey the concept that the preexisting condition has changed by including applicable descriptors (e.g., "more frequent headaches").

A3-7.9 LACK OF EFFICACY OR WORSENING OF MULTIPLE SCLEROSIS

Medical occurrences or symptoms of deterioration that are anticipated as part of the expected pattern of progression of the underlying disease, or other MS-related symptoms should not be recorded as adverse events. Clinical MS relapses will be recorded on a dedicated eCRF. However, deterioration that is judged by the investigator to have unexpectedly worsened in severity or frequency or changed in nature at any time during the study should be recorded as an adverse event. If there is any

Appendix 3: Adverse Events: Definitions and Procedures for Recording, Evaluating, Follow-Up, and Reporting

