uncertainty as to whether an event is due to disease progression, it should be reported as an adverse event. When recording an unanticipated worsening of MS on the Adverse Event eCRF, it is important to convey the concept that the condition has changed by including applicable descriptors. Occasional isolated symptoms that according to the investigator are caused by MS, but do not constitute a full MS relapse, should be reported as an adverse event, with the causality "Disease under study" (see Section [A3-5](#)).

A3-7.10 HOSPITALIZATION OR PROLONGED HOSPITALIZATION

Any adverse event that results in hospitalization (i.e., inpatient admission to a hospital) or prolonged hospitalization should be documented and reported as a serious adverse event (per the definition of serious adverse event in Section [A3-2](#)), except as outlined below.

An event that leads to hospitalization under the following circumstances should not be reported as an adverse event or a serious adverse event:

- Planned hospitalization required by the protocol unless prolonged
- Hospitalization for a preexisting condition, provided that all of the following criteria are met:

The patient was hospitalized for an elective procedure that was planned prior to the study, was scheduled during the study despite the fact that the condition had not worsened, or was scheduled during the study when treatment became necessary because of the expected normal progression of the condition. Such events should still be recorded as medical procedures in the On Study Surgeries and Procedures eCRF.

The patient has not experienced an adverse event

- Hospitalization following an MS relapse as long as the reason for hospitalization is to receive standard treatment with high dose corticosteroids

An event that leads to hospitalization under the following circumstances is not considered to be a serious adverse event, but should be reported as an adverse event instead:

- Hospitalization that was necessary because of patient requirement for outpatient care outside of normal outpatient clinic operating hours

Appendix 3: Adverse Events: Definitions and Procedures for Recording, Evaluating, Follow-Up, and Reporting

A3–7.11 CASES OF OVERDOSE , MEDICATION ERROR, DRUG ABUSE, OR DRUG MISUSE

Overdose (accidental or intentional), medication error, drug abuse, and drug misuse (hereafter collectively referred to as "special situations") are defined as follows:

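### Protocol A3-2 says a death from disease progression cannot be a serious adverse event, while A3-7.7 sends the same death down the immediate SAE reporting route; the rules on MS hospital stays are also not aligned

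*Protocol*

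**What the plan says.** All the relevant text is in Protocol Appendix 3, apart from the list of adverse events of special interest (AESIs) in Section 8.3.8 and the safety outputs in SAP Section 5.4.2.1.

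- **A3-1** takes the disease under study and its expected progression out of the adverse event definition, "including MS relapses, signs, or symptoms of the disease or disorder being studied, unless more severe than expected" for the patient.
- **A3-2** opens with a condition, "If an event is not an adverse event per the definition in Section" A3-1, and concludes that such an event cannot be an SAE, "even if serious conditions are met (e.g., hospitalization for signs or symptoms of the disease under study, death due to progression of disease").
- **A3-7.7** covers all deaths in the reporting period. These, "regardless of relationship to study treatment, must be recorded on the Adverse Event eCRF and immediately reported to the Sponsor", with a pointer to A3-5. It adds: "This includes death attributed to an MS relapse". "If the death is attributed solely to progression of multiple sclerosis", it names the term to enter on the Adverse Event eCRF.
- **A3-7.10** makes any adverse event that leads to hospitalization an SAE, subject to listed exceptions that are to be reported neither as an AE nor as an SAE. The MS exception is: "Hospitalization following an MS relapse as long as the reason for hospitalization is to receive standard treatment with high dose corticosteroids".
- **A3-7.9** directs that, where it is unclear whether an event is due to progression, it is reported as an adverse event.
- **SAP 5.4.2.1** summarizes SAEs, adverse events leading to death, and deaths with their cause.

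**The concern.** A site classifying an MS death finds one section that names it as a non-SAE and another that puts it on the SAE route. SAE status decides whether the 24-hour reporting clock and the sponsor's expectedness assessment (Protocol 8.3.4) apply, and whether the event enters the SAE summary. A fatal event could appear among adverse events leading to death and be absent from the SAE table, depending on which section the site applied.

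The same uncertainty, in weaker form, attaches to admissions for MS. These reflect disease activity, which the treatment is intended to change, so inconsistent classification need not fall evenly on the two arms. About 35 sites are planned for about 102 participants (Protocol A1-5), roughly three per site, so different readings at different sites are plausible.

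**Working it through.** The protocol states no figure to reproduce. The check is a comparison of the rules, followed by one calculation for scale.

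**Deaths**

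1. Under A3-1, expected MS progression is not an adverse event. Under A3-2, what is not an adverse event cannot be an SAE, and death from progression is given as an example.
2. Under A3-7.7, a death solely from MS progression is recorded on the Adverse Event eCRF and reported immediately through A3-5.
3. A3-5 sets the requirements for two classes only: SAEs and AESIs.
4. The AESI list in Section 8.3.8 consists of liver test categories and suspected transmission of an infectious agent by study treatment. An MS death is in neither.
5. So the only class under which A3-7.7 can send the death through A3-5 is SAE. A3-7.7 does not itself use that term; the status follows from steps 3 and 4.
6. Footnote d of Table A3-1 points the same way, since Grade 5 events must be reported as SAEs. It is supporting evidence only: the table is for events not listed in the CTCAE, and it defines Grade 5 as a death related to an adverse event.

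Steps 1 and 5 give opposite answers for the same death.

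**Hospital stays**

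| Case | A3-1 and A3-2 | A3-7.10 |
|---|---|---|
| Relapse of expected severity, admitted for standard high-dose corticosteroids | Not an AE, so not an SAE | Exempt |
| Relapse of expected severity, admitted for another reason | Not an AE, so not an SAE | Not exempt; reportable by implication only, because the rule starts from an adverse event |
| Relapse more severe than expected, admitted for standard high-dose corticosteroids | An AE that meets the hospitalization criterion | Exempt: reported neither as AE nor as SAE |
| Relapse more severe than expected, admitted for another reason | An AE that meets the hospitalization criterion | SAE |

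The first and last rows agree. In the second row the tension is implied: if every admission for expected MS symptoms were already outside the definition, an exemption limited to corticosteroid stays would do little work. In the third row the exemption removes an event that A3-1 and A3-2 include. A3-7.10 does present it as an exception to the SAE rule, but A3-1 has no matching exception for AE status.

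**Scale**

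Planned arm sizes are 68 fenebrutinib and 34 placebo (Protocol 9.2, SAP 3). One participant classified differently changes SAE incidence by:

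- placebo: 1/34 = 0.029, or 2.9 percentage points;
- fenebrutinib: 1/68 = 0.015, or 1.5 percentage points.

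**The case against.** The best defence is that the sections can be read together. A3-2 is conditional on A3-1, and A3-1 keeps MS events that are more severe than expected as adverse events. A reader might infer from the A3-2 examples that no MS hospital stay can ever be an SAE; the condition and the exception show that this is not so. Nor does A3-7.10 state that every MS admission outside the corticosteroid exemption is an SAE, because it begins from an adverse event. For hospital stays this defence largely succeeds, and what is left is an implied inconsistency. A3-7.9 narrows it further by resolving doubt toward adverse event reporting.

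For deaths the defence is weaker. It could be said that in participants aged 18 to 55 with EDSS up to 5.5, any MS death within 12 weeks is more severe than expected, hence an adverse event and an SAE. That may well be how most sites would reason. But A3-2 names this kind of death as a non-SAE, without repeating the exception, and A3-7.7 applies whatever the expected course.

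It is also fair to say that A3-7.7 is the specific, mandatory instruction and the A3-2 wording only an example. That makes it likely the death is reported, but it leaves the SAE status contradictory on paper.

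A reader might further infer that MS deaths could go unreported. The documents do not support that: A3-7.7 brings every death in the period to the sponsor immediately, and the SAP summarizes deaths and causes separately from SAEs. Clinical relapses also have a dedicated eCRF.

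**Conclusion.** The contradiction on deaths is real and should be corrected. A3-2 and A3-7.7 give a death from MS progression opposite SAE status; this conclusion rests on A3-5 covering only SAEs and AESIs and on the AESI list in Section 8.3.8. The hospital-stay inconsistency is secondary and implied.

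The practical size is small but cannot be quantified. MS deaths will be rare in this population and period. The documents give no expected number of MS deaths or MS admissions, and no relapse or hospitalization rate from which to derive one. A reader might infer a material shift in the SAE comparison between arms; the documents support only the per-participant figures of 2.9 and 1.5 points. The rules continue into the open-label extension, but that phase has no placebo group and so cannot affect the comparison. No alpha, power or sample size figure is involved.

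**What to change.** In A3-2, either remove the death example or add that all deaths are reported under A3-7.7 whatever their cause. Adding the sentence is the more complete option, because deletion alone leaves the general rule linking A3-2 to the A3-1 exclusion.

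Reconcile A3-1, A3-2 and A3-7.10 so that they state one rule on whether hospitalization for an MS relapse counts as an SAE, covering relapses more severe than expected and admissions for standard corticosteroids. Which rule to adopt is for the sponsor; the need is that the three sections agree.

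The cost is a short wording change in the next amendment and a memo to sites, with possibly a few more SAE reports. No SAP change is needed, since SAEs and deaths with their causes are already summarized.

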Appendix 4: Collection of Pregnancy Information

A4–1. PREGNANCIES IN FEMALE PARTICIPANTS

Female participants of childbearing potential will be instructed through the Informed Consent Form to immediately inform the investigator if they become pregnant during the study or within 4 weeks after the final dose of fenebrutinib. A paper Clinical Trial Pregnancy Reporting Form should be completed and submitted to the Sponsor or its designee immediately (i.e., no more than 24 hours after the investigator becomes aware of the pregnancy), either by faxing or by scanning and emailing the form, using the fax number or email address provided to investigators. Pregnancy should not be recorded on the Adverse Event eCRF. The investigator should discontinue study treatment and counsel the participant, discussing the risks of the pregnancy and the possible effects on the fetus. Monitoring of the participant should continue until conclusion of the pregnancy. Any serious adverse events associated with the pregnancy (e.g., an event in the fetus, an event in the mother during or after the pregnancy, or a congenital anomaly or birth defect in the child) should be reported on the Adverse Event eCRF. In addition, the investigator will submit a Clinical Trial Pregnancy Reporting Form when updated information on the course and outcome of the pregnancy becomes available.

Attempts should be made to collect and report infant health information. When permitted by the site, an Authorization for the Use and Disclosure of Infant Health Information would need to be signed by one or both parents (as per local regulations) to allow for follow-up on the infant. If the authorization has been signed, the infant's health status at birth should be recorded on the Clinical Trial Pregnancy Reporting Form. In addition, the Sponsor may collect follow-up information on the infant's health status at 6 and 12 months after birth.

A4–2. PREGNANCIES IN FEMALE PARTNERS OF MALE PARTICIPANTS

Male participants will be instructed through the Informed Consent Form to immediately inform the investigator if a female partner becomes pregnant during the study or within 4 weeks after the final dose of fenebrutinib. The investigator should report the pregnancy on the paper Clinical Trial Pregnancy Reporting Form and submit the form to the Sponsor or its designee immediately (i.e., no more than 24 hours after learning of the pregnancy), either by faxing or by scanning and emailing the form using the fax number or email address provided to investigators. Attempts should be made to collect and report details of the course and outcome of any pregnancy in the partner of a male participant exposed to study treatment. When permitted by the site, the pregnant partner would need to sign an Authorization for the Use and Disclosure of Pregnancy Health Information to allow for follow-up on her pregnancy. If the authorization has been signed, the investigator should submit a Clinical Trial Pregnancy Reporting Form with additional information on the pregnant partner and the course and outcome of the pregnancy as it becomes available.

Appendix 4: Collection of Pregnancy Information

Attempts should be made to collect and report infant health information. When permitted by the site, an Authorization for the Use and Disclosure of Infant Health Information would need to be signed by one or both parents (as per local regulations) to allow for follow-up on the infant. If the authorization has been signed, the infant's health status at birth should be recorded on the Clinical Trial Pregnancy Reporting Form. In addition, the Sponsor may collect follow-up information on the infant's health status at 6 and 12 months after birth.

An investigator who is contacted by the male participant or his pregnant partner may provide information on the risks of the pregnancy and the possible effects on the fetus, to support an informed decision in cooperation with the treating physician and/or obstetrician.

A4-3. ABORTIONS

A spontaneous abortion should be classified as a serious adverse event (as the Sponsor considers abortions to be medically significant), recorded on the Adverse Event eCRF, and reported to the Sponsor immediately (i.e., no more than 24 hours after the investigator becomes aware of the event; see Section [A3-5](#)).

If a therapeutic or elective abortion was performed because of an underlying maternal or embryofetal toxicity, the toxicity should be classified as a serious adverse event, recorded on the Adverse Event eCRF, and reported to the Sponsor immediately (i.e., no more than 24 hours after the investigator becomes aware of the event; see Section [A3-5](#)). A therapeutic or elective abortion performed for reasons other than an underlying maternal or embryofetal toxicity is not considered an adverse event.

All abortions should be reported as pregnancy outcomes on the paper Clinical Trial Pregnancy Reporting Form.

A4-4. ABNORMAL PREGNANCY OUTCOMES

Abnormal pregnancy outcomes (e.g., spontaneous abortion, fetal death, stillbirth, congenital anomaly, birth defect, ectopic pregnancy) in a female participant exposed to study treatment or the female partner of a male participant exposed to study treatment should be classified as a serious adverse event, recorded on the Adverse Event eCRF, and reported to the Sponsor immediately (i.e., no more than 24 hours after the investigator becomes aware of the event; see Section [A3-5](#)).

Appendix 5

Genetics: Use and Analysis of DNA

Genetic biomarker assessments will not be performed in this study.

Appendix 6

Safety Plan: Management of Identified and Potential Risks

Fenebrutinib is not approved, and clinical development is ongoing. The safety plan for participants in this study is based on clinical experience with fenebrutinib in completed and ongoing studies. The anticipated important safety risks for fenebrutinib are outlined below. Please refer to the Fenebrutinib Investigator's Brochure for a complete summary of safety information.

Several measures will be taken to ensure the safety of study participants. Eligibility criteria have been designed to exclude individuals at higher risk for toxicities. Participants will undergo safety monitoring during the study, including assessment of the nature, frequency, and severity of adverse events. In addition, guidelines for managing adverse events, including criteria for treatment interruption or discontinuation, are provided below.

A6-1. RISKS ASSOCIATED WITH FENEBRUTINIB

A6-1.1 HEPATIC TRANSAMINASE ELEVATIONS

In clinical Phase 2 studies to date, participants treated with fenebrutinib have been found to be at an increased risk of transaminase elevations than participants on placebo.

Between 1% and 10% of participants in the fenebrutinib 200 mg BID treatment arms of blinded randomized studies and OLEs experienced Grade 2 or higher transaminase elevations (ALT/AST of 3-5 × ULN or higher), compared with fewer than 1% of participants in the placebo arms across studies.

Participants enrolled in clinical trials with fenebrutinib will be monitored for the risk of hepatotoxicity with regular measurement of transaminases as outlined in the schedules of activities (see [Table 1](#)). They should receive appropriate supportive care as clinically indicated, with hepatotoxicity managed in accordance with the study protocols and site institutional guidelines. Cases of potential drug-induced liver injury that include *the categories below must be reported to Sponsor as an adverse event of special interest within 24 hours of awareness (see Section 8.3.8).*

- *Cases of elevated ALT or AST (3 × ULN) in combination with either an elevated total bilirubin (>2 × ULN) or clinical jaundice, as defined by Hy's Law (see [A3□7.6](#))*
- *Cases of an elevated ALT and/or AST 3–5 × ULN, INR > 1.5, total bilirubin ≤ 2 × ULN, and absence of clinical jaundice*
- *Cases of elevated ALT and/or AST 5-8 × ULN, total bilirubin ≤ 2 × ULN and absence of clinical jaundice*
- *Cases of elevated ALT and/or AST > 8 × ULN, total bilirubin ≤ 2 × ULN and absence of clinical jaundice*

